-------------	------------------------------------------------------------------------------------------------------------------------------------------------------------------------------------------------------------------------------------------------------------------------------------------------------------------------------------------------------------------------------------------------------------------------------------------------------------------------------------------------------------------------------------------------------------------------------------------------------------------------------------------------------------------------------------------------------------------------------------------------------------------------------------------------------------------------------------------------------------------------------------------------------------------------------------------------------------------------------------------------------------------------------

Follow up	
The follow-up period was from the beginning of the study to the first outcome event (death or cardiovascular event, peritoneal dialysis-associated peritonitis). For patients who did not have an outcome event or survived, the follow-up period is 1 year. The lymphocyte / monocyte ratio should be tested every 3 months after the start of the study, and the final value is the average.

Exposure factor	Monocyte / lymphocyte ratio (MLR)
Outcome Measures	
Primary Outcome Measure:
 
 • All-cause mortality • Cardiovascular mortality 
Secondary Outcome Measure:
 
 • The Incidence of cardiovascular events (including acute heart failure, angina, acute myocardial infarction, arrhythmias requiring treatment, transient ischemic attack (TIA), cerebral infarction or cerebral hemorrhage, peripheral vascular disease) • The Incidence of peritoneal dialysis-associated peritonitis

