
Statistical plan
	
Statistical hypothesis: test hypothesis H0: $\lambda 1 = \lambda 2$, that is, there is no difference in mortality and the Incidence of cardiovascular events between the high MLR group and the low MLR group.
 
Alternative hypothesis H1: $\lambda 1 \neq \lambda 2$, there is a statistical difference in mortality and the Incidence of cardiovascular events between the high MLR group and the low MLR group.
 
Main statistical analysis methods: Spss23.0 software was used for data statistical analysis. The continuity variables were tested for normality first. The continuous variables of normal distribution are represented by 'x \pm s'; the continuous variables of skew distribution are represented by median m; the data of classification or counting type are displayed by percentage. Two independent samples were used to compare the differences between groups in normal distribution measurement data, Mann Whitney U test was used to compare the differences between groups in non normal distribution measurement data, and chi square test was used to compare the differences between groups in classification or counting data. For missing values such as missing values and censored values, when the missing values are concentrated in a few variables and these variables are not the main variables for analysis, deletion can be considered, or the mean substitution method can be used to find alternative values for the missing values. The correlation between MLR and other indexes was analyzed by Spearman correlation and linear regression. Kaplan Meier curve was drawn to estimate the survival rate and cardiovascular disease incidence rate, and log rank test was used to check the difference. Single factor and multiple factor Cox regression models were used to explore the independent risk factors of death and cardiovascular disease in peritoneal dialysis patients, and to evaluate the correlation between MLR level and clinical all-cause and cardiovascular disease-related survival outcomes in peritoneal dialysis patients. Using HR risk ratio (95% CI confidence interval) to show the results, bilateral

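### The missing-data rule counts censored times as missing and allows mean substitution for undefined non-main variables; the numerical effect is small to modest, and the wording is easily corrected

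*Combined protocol and SAP*

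**What the plan says.** All of this is in the Summary table of the combined protocol and SAP.

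- **Statistical plan, the rule.** It begins "For missing values such as missing values and censored values, when the missing values are concentrated in a few variables", which makes a censored value one kind of missing value. The first remedy is conditional: "when the missing values are concentrated in a few variables and these variables are not the main variables for analysis, deletion can be considered". A second remedy, single imputation, is offered as an alternative under the same condition: "the mean substitution method can be used to find alternative values for the missing values". The row does not define a main variable and does not say whether deletion removes patients or variables.
- **Statistical plan, the analyses.** For the outcomes, "Kaplan Meier curve was drawn to estimate the survival rate and cardiovascular disease incidence rate", with a log-rank test. For adjustment, "Single factor and multiple factor Cox regression models were used to explore the independent risk factors of death and cardiovascular disease". Separately, "The correlation between MLR and other indexes was analyzed by Spearman correlation and linear regression".
- **Follow up.** "For patients who did not have an outcome event or survived, the follow-up period is 1 year". No end date is given for a patient lost earlier.
- **Sample size.** Loss of at most 5% per group is assumed, and this is used only to raise the number of patients.

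**The concern.** Two things look wrong.

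First, a patient who leaves follow-up alive contributes known event-free time. Kaplan-Meier, log-rank and Cox all use that time directly. A rule that treats it as a gap to be deleted or filled contradicts the methods named a few lines later in the same row.

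Second, single mean substitution gives every patient with a missing value the same covariate value. Among those patients the Cox model cannot adjust for the covariate. If the covariate is related to both MLR and death, part of its effect is credited to MLR, although the model is meant to identify independent risk factors. Mean-filled values also weaken rank correlations. Because main is undefined, the plan does not say whether the Cox covariates are protected from this.

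**Working it through.** The plan gives no figure for the effect of missing data, so there is none to reproduce directly. Its sample-size figure confirms the inputs: 90.7% against 98.6%, two-sided 0.05, 80% power and a pooled-variance comparison of two proportions give 127 per group, and 127 × 1.05 = 133.35, against the stated 133.

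**1. Censoring.** Inputs from the Sample size row: 133 per group; one-year survival 86.6% and 97% (all-cause), 90.7% and 98.6% (cardiovascular); 5% loss.

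- Expected deaths: 133 × (0.134 + 0.030) = 21.8. Expected cardiovascular deaths: 133 × (0.093 + 0.014) = 14.2.
- HR = ln(1 − pH)/ln(1 − pL): ln(0.866)/ln(0.970) = 4.72, and ln(0.907)/ln(0.986) = 6.92.
- Deleting a share c of event-free patients changes a risk p to p/(1 − c(1 − p)). With c = 0.05, 0.134/0.9567 = 0.140 and 0.030/0.9515 = 0.032, so the HR is 4.71. For cardiovascular death, 0.093 becomes 0.097 and 0.014 becomes 0.015, so the HR is 6.91.
- Deletion in one group only gives 4.49 to 4.95 (all-cause) and 6.58 to 7.27 (cardiovascular). On the log scale the all-cause shift is about 0.05. The standard error from 17.8 and 4.0 expected deaths is √(1/17.8 + 1/4.0) = 0.55, so the shift is about a tenth of it.

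**2. Mean-filled covariate.** The documents give none of these inputs, so all are assumed: true adjusted HR 1.0; one confounder; values missing completely at random; one-year risk 8.2% (the mean of 13.4% and 3.0%). Mild is correlation 0.3 with MLR and HR 1.5 per SD; moderate is 0.5 and 2.0; strong is 0.5 and 2.46. Cox models were fitted to 20 simulated samples of 40,000 per scenario. The table shows the range from mild to strong.

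| Handling | HR per SD of MLR | HR, median split |
|---|---|---|
| Mean-filled, 10% missing | 1.01–1.06 | 1.02–1.09 |
| Mean-filled, 20% missing | 1.03–1.12 | 1.04–1.19 |
| Mean-filled, 30% missing | 1.04–1.17 | 1.06–1.28 |
| Patients deleted | 0.98–1.01 | not tabulated |
| Covariate dropped | 1.13–1.55 | 1.22–2.02 |

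A closed form for the per-SD column is exp(βρm/(1 − (1 − m)ρ²)), with β the log HR per SD of the confounder, ρ its correlation with MLR and m the missing fraction. Moderate, 30% missing: exp(0.693 × 0.5 × 0.3/(1 − 0.7 × 0.25)) = exp(0.104/0.825) = 1.13. Mild and strong give 1.04 and 1.18, in line with the simulation.

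**3. False-positive rate for MLR** with 266 patients and about 22 deaths (Wald test, 3,000 to 4,000 samples per scenario; mild/moderate/strong).

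- Per SD: 4.9–5.6% with no missing data; 6.0/8.3/10.5% with 30% mean-filled.
- Median split: about 4.9/3.7/4.5% with no missing data; about 5.0/5.4/7.0% with 30% mean-filled.

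**4. Spearman correlations.** With 400,000 simulated pairs, mean-filling one variable reduces the coefficient to 0.94/0.87/0.80 of its true value at 10/20/30% missing for a normal variable, and to about 0.92/0.84/0.76 for a skewed one.

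**The case against.** The rule limits itself to variables that are not main. Death and cardiovascular events are the main research purpose, the subject of the hypotheses and the listed outcomes, so its own condition very probably excludes them. Choosing Kaplan-Meier and Cox implies right-censoring in the usual way. Censored values might also mean laboratory results outside assay limits. Most of this stands, and it is why the censoring part is an error of wording and not evidence that outcomes will be imputed. It does not rescue the sentence: the only place that mentions censored values classes them as missing, early loss has no stated end date, and mean substitution would not suit assay-limit values either.

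On covariates, every input above is assumed, the wording is permissive, and on the plan's own median grouping the false-positive rate stays near nominal except in the strong scenario. That also stands and limits the claim to a modest effect.

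A reader might go further and infer that the MLR result could be badly inflated, with an HR near 2 under the null. That needs a strong confounder to be judged non-main and dropped. The plan does not say this would happen, and deletion may equally mean removing patients, which gave no bias here.

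A reader might also infer that CRP or IL-6 will be the incomplete confounder. The Background calls such markers costly and hard to measure, but Data Sources lists both for collection, and nothing says that they enter the Cox model or will be incomplete. The Background also describes a cycle between blood cells and inflammation, so not all of their effect need be confounding.

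**Conclusion.** The concern holds as a minor one. Listing censored values as missing is wrong for the planned survival analyses. At the planned event rates and 5% loss it changes almost nothing, provided loss is unrelated to outcome. The loss allowance (5% of 266, about 13 patients) is close to the 14 expected cardiovascular deaths, so outcome-related loss could matter more, but it would do so under correct censoring as well.

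Mean substitution is a poor default for a Cox covariate. With up to 30% missing, and the assumed confounder strengths, the bias in the MLR hazard ratio is at most about 17% per SD or 28% for the split. It shrinks quickly with less missing data or weaker confounding. The shrinkage of the Spearman correlations needs no confounding and affects a secondary, descriptive analysis. The documents do not support a claim that the primary comparison is invalid.

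**What to change.** In the Statistical plan row:

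1. Delete 'and censored values' from the missing-data rule.
2. State that patients without the event being analysed are right-censored at last contact or at 1 year, whichever is first, and are never deleted or imputed.
3. State that covariates of the multivariable Cox model are main variables and are not mean-filled or dropped because of missing values.
4. Replace mean substitution with multiple imputation, with the event indicator and cumulative hazard in the imputation model, and give complete-case analysis as a sensitivity analysis. In the three scenarios at 30% missing, this imputation gave an HR equal to the no-missing fit (ratio 1.00). Complete-case analysis was also unbiased under these assumptions, but its standard error rose by about 6% at 10% missing and 21% at 30%. Three covariates each 10% missing independently would keep 0.9³ = 73% of patients and about 16 of 22 deaths.
5. Compute the Spearman correlations on observed pairs.

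The cost is a few sentences and a little more analysis work. No new data are needed.

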Research hypothesis	The level of MLR is related to the prognosis of patients with peritoneal dialysis. High levels of MLR may increase the risk of death, cardiovascular events and dialysis-associated peritonitis in patients with peritoneal dialysis.
Study Model	prospective cohort study

Sample size	
This study is based on a balanced control design of two groups to test whether there is a significant difference in survival rates. All-cause mortality and cardiovascular mortality are Primary Outcome Measures. Divided into high MLR group and low MLR group according to the median of monocyte / lymphocyte ratio (MLR). The previous research results show that the one-year survival rate of patients in the high MLR group was 86.6%, and the survival rate of patients in the low MLR group was 97%. Taking 0.05 as the statistical significance level on both sides, setting the test efficiency to 80%, adopting a 1: 1 balanced design, calculated by software PASS.11, it requires 84 cases in the high MLR group and 84 cases in the low MLR group. The one-year cardiovascular survival rate of patients in the high MLR group is 90.7%, and the cardiovascular survival rate of patients in the low MLR group 98.6%, taking 0.05 as the statistical significance level on both sides, setting the test efficiency to 80%, adopting a 1: 1 balanced design, calculated by software PASS.11, 127 cases are required in the high MLR group and 127 cases are in the low MLR group. Further assuming that the maximum rate of lost follow-up in each group will not exceed 5%, the final sample size is determined as 133 cases in the high MLR group and 133 cases in the low MLR group, for a total of 266 cases.

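### Kaplan-Meier is planned for cardiovascular incidence although deaths from other causes compete, so absolute incidence is overstated, by about 0.2 points for one-year cardiovascular death

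*Combined protocol and SAP*

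**What the plan says.** The relevant text is in the Summary table of the combined protocol and SAP.

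- **Statistical plan, estimation:** a "Kaplan Meier curve was drawn to estimate the survival rate and cardiovascular disease incidence rate".
- **Statistical plan, testing and modelling:** "log rank test was used to check the difference", and "Single factor and multiple factor Cox regression models were used to explore the independent risk factors of death and cardiovascular disease". Results are to be reported as hazard ratios.
- **Statistical plan, hypothesis:** the null is λ1 = λ2, explained as "there is no difference in mortality and the Incidence of cardiovascular events between the high MLR group and the low MLR group".
- **Outcome Measures:** all-cause and cardiovascular mortality are primary. The incidence of cardiovascular events is secondary, and the list of event types does not name cardiovascular death.
- **Sample size:** one-year all-cause survival of 86.6% (high MLR) and 97% (low MLR), and one-year cardiovascular survival of 90.7% and 98.6%.
- **Follow up:** for patients without an outcome event, "the follow-up period is 1 year".

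The Background attributes about half of deaths in peritoneal dialysis patients to cardiovascular disease. The plan does not say how death from another cause is handled when a cardiovascular outcome is analysed, and it names no cumulative incidence function or other competing-risk method.

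**The concern.** The stated target is an incidence: the share of patients who have a cardiovascular death or event within a year. Kaplan-Meier with other deaths censored estimates something else, namely the share who would have the event if nobody could die of anything else. Because censored patients are treated as still at risk, 1-KM exceeds the actual incidence whenever other deaths occur, and by more where they are more frequent.

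Here other-cause death is common by the plan's own account, and on the Sample size figures it is higher in the high-MLR group. The absolute one-year incidences, and the gap between the two curves, would therefore be reported too high. Those are the figures a clinical reader would take away as the risk attached to a high MLR.

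**Working it through.** **Inputs.** All-cause survival S: 0.866 (high), 0.970 (low). Cardiovascular survival S_cv: 0.907 (high), 0.986 (low). Both are from the Sample size row. Hazards are assumed constant over the year.

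**Reproducing the plan's figure.** Two-sided 0.05, 80% power, two proportions with pooled variance under the null:

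n = [1.960 × √(2 × 0.9465 × 0.0535) + 0.8416 × √(0.907 × 0.093 + 0.986 × 0.014)]² / 0.079² = (0.6237 + 0.2637)² / 0.006241 = 126.2, so 127 per group, as stated.

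The plan thus used the cardiovascular survival rates as simple proportions. It does not say whether they were originally crude or Kaplan-Meier figures, so both readings follow.

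**Reading A: the rates are Kaplan-Meier estimates.** Cardiovascular hazard h_cv = −ln S_cv; total hazard h = −ln S; other-cause hazard = h − h_cv; cumulative incidence = (h_cv / h) × (1 − S).

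- High: h_cv = 0.0976, h = 0.1439, other-cause 0.0463. Incidence = 0.0976 / 0.1439 × 0.134 = 9.09%; 1-KM = 9.30%.
- Low: h_cv = 0.0141, h = 0.0305, other-cause 0.0164. Incidence = 0.0141 / 0.0305 × 0.030 = 1.39%; 1-KM = 1.40%.
- Difference: 7.70 points, against 7.90 by 1-KM.

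**Reading B: the rates are crude.** Incidence is then 9.30% and 1.40%, and other-cause death is 13.4 − 9.3 = 4.1% and 3.0 − 1.4 = 1.6%. Here h_cv = h × (cardiovascular deaths / all deaths), and 1-KM = 1 − exp(−h_cv).

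- High: 0.1439 × 0.093 / 0.134 = 0.0999; 1-KM = 9.50%.
- Low: 0.0305 × 0.014 / 0.030 = 0.0142; 1-KM = 1.41%.
- Difference: 7.90 points, against 8.09 by 1-KM.

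Either way the high-MLR incidence and the group difference are each overstated by about 0.2 points.

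**Cardiovascular events.** No rate is stated, so a range is assumed. Competing hazards are taken from reading A: non-cardiovascular deaths only (0.0463 v 0.0164), or all deaths (0.1439 v 0.0305). The second case applies if a fatal cardiovascular event without a prior listed event does not count. It uses the overall death hazard for event-free patients and so probably sits at the high end. Differences are taken before rounding.

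| Assumed 1-KM, high v low | Difference by 1-KM | Only non-cardiovascular deaths compete | All deaths compete |
|---|---|---|---|
| 20% v 10% | 10.0 | 19.6% v 9.9%, 9.6 | 18.7% v 9.8%, 8.8 |
| 30% v 15% | 15.0 | 29.4% v 14.9%, 14.5 | 28.1% v 14.8%, 13.3 |
| 40% v 20% | 20.0 | 39.2% v 19.8%, 19.3 | 37.5% v 19.7%, 17.8 |

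The difference is overstated by about 4% in relative terms in the first case and about 13% in the second.

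**The case against.** **The only effect that the documents' figures allow to be computed is trivial.** With 133 per group, the standard error is about √(0.093 × 0.907 / 133) = 2.5 points for the high-MLR incidence, and about √(0.025² + 0.010²) = 2.7 points for the difference. A bias of 0.2 points is under a tenth of either and would not change a conclusion. This stands for cardiovascular mortality. For cardiovascular events the effect could be larger, but only at assumed rates.

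**The planned inference is not affected.** The null is stated in hazards, and with other deaths censored the log-rank test and the Cox hazard ratio compare cause-specific hazards. This stands in full. Testing cumulative incidence instead would answer a different question: with the same cardiovascular hazard in both groups (0.2231, or 20% by 1-KM) and all-death hazards of 0.1439 and 0.0305 competing, cumulative incidence would be 18.7% v 19.7% although λ1 = λ2.

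**An overstated difference is not a general property of Kaplan-Meier.** Correct. It follows here from the pattern in the Sample size row. If the competing hazard were instead 0.05 in the high group and 0.4 in the low group, with 1-KM of 20% v 10%, cumulative incidence would be 19.5% v 8.3%. The difference would then be 11.3 points (before rounding), and 1-KM would understate it.

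**Peritonitis.** Because follow-up runs "to the first outcome event (death or cardiovascular event, peritoneal dialysis-associated peritonitis", a reader might infer that peritonitis is a further competing event and that the overstatement is much larger. The documents do not support that. A patient with peritonitis can still have, or die of, a cardiovascular event; the rule only ends observation. That is censoring, possibly informative. If cardiovascular risk is unchanged afterwards, Kaplan-Meier still returns 9.3% v 1.4%, setting other deaths aside. If the cardiovascular hazard doubles after peritonitis, at an assumed peritonitis hazard of 0.1 to 0.4 per year, the true figures are 9.7–10.8% v 1.5–1.6%, and Kaplan-Meier understates them. The bias may be nil or run the other way, and a cumulative incidence estimator does not repair it. The follow-up rule needs its own treatment.

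**Conclusion.** The concern holds in a limited form. The planned estimator does not match its stated target: 1-KM overstates absolute cardiovascular incidence because other-cause deaths are censored and, on the plan's own rates, slightly overstates the absolute group difference. The size is about 0.2 points for one-year cardiovascular mortality under either reading of the stated rates. For cardiovascular events at an assumed 20% v 10%, the excess in the difference is 0.4 to 1.2 points, depending on which deaths compete.

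These figures assume constant hazards, and those for events rest on assumed rates. The direction for the group difference rests on other-cause death being higher in the high-MLR group, as the Sample size row implies. The point concerns the reported absolute curves and rates only. It does not touch the sample size, the log-rank test or the Cox models, and it gives no ground for treating peritonitis as a competing event.

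**What to change.** In the Statistical plan row:

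1. Estimate cardiovascular mortality by the Aalen-Johansen cumulative incidence function, with non-cardiovascular death as the competing event.
2. Estimate the incidence of cardiovascular events in the same way, with any death without a prior event as competing. State whether a fatal cardiovascular event counts as an event.
3. Keep the log-rank test and Cox models for these outcomes, and label their results as cause-specific.
4. Keep Kaplan-Meier for all-cause survival.

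The cost is a few lines of text and one routine that may lie outside SPSS 23.0. No new data are needed, since cause of death is already required for a primary outcome. The reported incidence figures will be slightly lower. Ending follow-up at peritonitis should be dealt with separately.

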Data Sources	
Use a combination of electronic medical record system, test report system, national peritoneal dialysis information registration system, cardiovascular event registration form to collect patient clinical and demographic data, laboratory data, and survival outcomes. For out-of-hospital events, relevant information is obtained by telephone follow-up.
 
Clinical and demographic data : age, gender, body mass index (BMI), dialysis time, smoking history, family history, medication history, medication status, primary kidney disease and complications
 
Laboratory data: Peritoneal balance test (PET), dialysis adequacy assessment (KT/v), c-reactive protein (CRP), erythrocyte sedimentation rate (ESR), procalcitonin (PCT), interleukin 6 (IL-6), whole blood count and classification of leukocyte count, calcium, phosphorus, intact parathyroid hormone (IPTH), serum iron, ferritin, transferrin, transferrin saturation, urea nitrogen, serum creatinine, uric acid, urinary protein ,estimated glomerular filtration rate (eGFR), blood glucose, total cholesterol, triglyceride, high-density lipoprotein, low-density lipoprotein, albumin (ALB), N-terminal pro-brain natriuretic peptide, pulse pressure (PP), blood pressure,(BP) , left ventricular mass index (LVMI), ejection fraction (EF), carotid artery intima-media thickness (IMT).

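### With about 22 deaths and 14 cardiovascular deaths expected, the planned ordinary Cox models need a short pre-set adjustment list and a method that still works if the low-MLR group has no cardiovascular death

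*Combined protocol and SAP*

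**What the plan says.** All of this is in the Summary table.

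- **Statistical plan.** "Single factor and multiple factor Cox regression models were used to explore the independent risk factors of death and cardiovascular disease". The same sentence gives these models a second task: to evaluate MLR against all-cause and cardiovascular survival. Results are to be shown as hazard ratios with 95% intervals, and every test uses two-sided p < 0.05. No covariate list, entry rule, cap on covariates or fallback for sparse events is given.
- **Data Sources.** The clinical and demographic items begin "age, gender, body mass index (BMI), dialysis time, smoking history, family history, medication history, medication status" and number 10. The laboratory list adds 31, counting the blood count with its leukocyte classification as one item and blood pressure as one. That makes 41. The row does not say which items are candidates for the Cox models.
- **Sample size.** "Divided into high MLR group and low MLR group according to the median of monocyte / lymphocyte ratio (MLR"). One-year survival is taken as 86.6% (high) and 97% (low), and one-year cardiovascular survival as 90.7% (high) and 98.6% (low). The total is 133 + 133 = 266. No expected number of deaths is stated.
- **Outcome Measures.** All-cause and cardiovascular mortality are both primary. Non-fatal cardiovascular events fall under a secondary outcome.

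**The concern.** A Cox model draws its information from events, not from patients. The study is sized for an unadjusted two-group comparison, and the rates behind that sizing leave few events for anything more.

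Two things are at stake. First, the planned cardiovascular effect is so large, and the low-group rate so small, that the low group may have no cardiovascular death. Ordinary Cox regression then cannot supply the hazard ratio and interval that the plan promises for a primary outcome. Second, a search for independent factors with so few events, without a rule fixed beforehand, can list noise as findings and lets the adjusted MLR estimate depend on which covariates happen to be chosen. Nothing in the plan keeps monocyte and lymphocyte counts, the numerator and denominator of MLR, out of the model for MLR.

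**Working it through.** **1. The plan's own figure.** Cardiovascular survival 0.907 v 0.986, two-sided 0.05, 80% power, 1:1, pooled variance, no continuity correction. Event rates are 0.093 and 0.014, with mean 0.0535.

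n = [1.96 √(2 × 0.0535 × 0.9465) + 0.8416 √(0.093 × 0.907 + 0.014 × 0.986)]² / 0.079² = 126.2, so **127 per group**, as stated. Then 127 × 1.05 = 133.35, which agrees with the stated 133.

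**2. Expected events in one year** (n × (1 − survival)).

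| Outcome | High MLR | Low MLR | Total |
|---|---|---|---|
| Death | 133 × 0.134 = 17.8 | 133 × 0.030 = 4.0 | 21.8 |
| Cardiovascular death | 133 × 0.093 = 12.4 | 133 × 0.014 = 1.9 | 14.2 |

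At 127 per group the totals are 20.8 and 13.6.

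**3. Chance of an empty low group.** For cardiovascular death, 0.986^133 = **15.3%** (0.986^127 = 16.7%). For all-cause death, 0.97^133 = 1.7%. When every event is in the high group, each event adds a factor e^β / (h e^β + l) to the partial likelihood, where h and l are the numbers at risk in the high and low groups. This rises with β without limit, so there is no finite maximum. Adding covariates does not change that. In simulations under the planned cardiovascular effect, 15% to 18% of fits had no finite MLR hazard ratio.

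**4. Events per covariate.** With 5 covariates: 21.8/5 = 4.4 deaths and 14.2/5 = 2.8 cardiovascular deaths each. With 10: 2.2 and 1.4.

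**5. False factors in a data-driven search.** The plan states no rule, so one has to be assumed: a single-factor screen, after which the survivors enter a multiple-factor Cox model and are judged at p < 0.05. All covariates are simulated with no effect.

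| Assumed screen | Covariates | Assumed correlation | Studies with at least one false factor |
|---|---|---|---|
| p < 0.10 | 41 | 0 | 85–86% |
| p < 0.10 | 41 | 0.2 | 57–59% |
| p < 0.10 | 20 | 0 | 61–65% |
| p < 0.10 | 20 | 0.2 | 42–43% |
| p < 0.05 | 40 plus MLR | 0 | 80% (death), 78% (cardiovascular death) |
| p < 0.05 | 40 plus MLR | 0.5 | at least 23% and at least 21% |

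The last row is a lower bound, because runs that selected 12 or more variables were counted as having no false factor. As a cross-check, 41 independent null tests at 0.05 give 1 − 0.95^41 = 88%, with 2.05 false positives expected. Where the type I error for MLR itself was examined (p < 0.10 screen), it was not inflated.

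**6. Follow-up rule.** The Follow up row ends follow-up at the first outcome event, peritonitis included. If that also stops the counting of deaths, and a share c of patients has an earlier event at a constant rate independent of death, the fraction of deaths kept is about c / (−ln(1 − c)). For an assumed c of 20% to 40% this is 0.90 to 0.78, leaving about 17–20 deaths and 11–13 cardiovascular deaths.

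**The case against.** - **No search procedure is stated.** The plan gives no screening sequence and does not tie the Cox models to the Data Sources row; some of those items may serve only the planned correlation of MLR with other indexes. A reader might infer that all 41 items enter one model, at 0.53 deaths and 0.35 cardiovascular deaths per item. The documents do not say so: 41 is a possible pool. This objection stands, and it is why the false-factor figure is a wide range. The all-null premise is also a simplification, since the Background treats CRP and interleukins as established predictors.
- **The non-finite hazard ratio is not caused by adjustment, and it is conditional.** It arises equally in the unadjusted model, and only if MLR enters as the median split. The Statistical plan speaks of the MLR level and the Follow up row averages repeated values, so a continuous MLR is possible; an empty low group would not then by itself make the estimate infinite. This stands. The median split is nevertheless the comparison in the sample size and in the stated hypotheses.
- **The main comparison survives.** A reader might infer that the MLR finding itself would be spurious. The documents and the calculations do not support that: the log-rank test works with no events in one group, and type I error for MLR was not shown to be inflated.
- **Cardiovascular disease may include non-fatal events.** These would add events, but the documents give no rate for them. The count of 14 applies to cardiovascular mortality, which is a primary outcome.
- **Few covariates means less control of confounding, and CRP and IL-6 can be argued either way.** The Background describes a vicious cycle in which cytokines both drive and follow the cell changes, so they may be confounders or lie on the pathway. This stands, and it shapes the fix.

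**Conclusion.** The point holds in this limited form. On the plan's own rates, about 22 deaths and 14 cardiovascular deaths cannot support an open-ended multiple-factor search for independent risk factors. With MLR split at the median, the stated method has about a 15% chance of giving no finite hazard ratio for cardiovascular mortality. That 15% rests only on the 98.6% low-group rate, 133 patients and the median split. The false-factor range of about 20% to 86% rests on an assumed screening threshold, number of variables and correlation, and should be read as a material risk rather than an estimate.

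This is more than a missing covariate list: naming a long list would cure neither the shortage of events nor the empty-group problem. It does not undermine the sample size, the log-rank comparison or the type I error for MLR. It should be settled before the data are analysed.

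**What to change.** 1. Estimate the MLR hazard ratio for all-cause and cardiovascular mortality by Firth-penalised Cox regression with profile-likelihood intervals. The estimate stays finite when one group has no events, although the interval will be wide.
2. Adjust for a short covariate set, named in advance, taken from baseline values of data already collected and sized to the expected events. As an illustration, MLR plus two covariates gives 14.2/3 = 4.7 cardiovascular deaths per term, and MLR plus three gives 21.8/4 = 5.5 deaths per term. The exact number is a judgement between stability and confounding, and the reason for it should be written down.
3. Keep monocyte and lymphocyte counts out of that model.
4. Report fuller adjustment as sensitivity analyses, including models with and without CRP and IL-6.
5. Label the wider risk-factor search exploratory, state its selection rule, and make no claim that the factors found are independent.

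**Cost.** New wording in the Statistical plan, and possibly software other than SPSS 23.0 for the penalised model. No additional patients or measurements are needed. The drawback is that the primary model adjusts for fewer confounders, which the sensitivity models address only in part.
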